Operating characteristics for simulations with control response probabilities in $\{0.2, 0.3, 0.4, 0.5, 0.6, 0.7\}$ are included at the end of this section.

Decision Rules

The decision rules of the trial at each analysis can be characterized in terms of the observed effect sizes (# responders / # subjects enrolled) in each arm. The effects leading to either futility or success, colored by result, are shown in Figure 2.

Figure 2: Scatterplots of the observed response rates for both arms, colored by result.

The design has a clear decision boundary at the first interim, declaring futility or success when the observed treatment effect is sufficiently large or small. The gap between success and futility narrows at the 2nd interim, as more information about the arms informs decision making. The effect size required to win is smallest at the final interim.

Operating Characteristics with No Borrowing

For comparison we include the operating characteristics of an alternate design without borrowing. This design uses the same interim schedule as the borrowing design but does not include stopping for futility. Table 6 compares the cumulative probability of declaring success for at each interim for both designs when the simulated control response rate is 0.45.

Table 6: Operating characteristics for the borrowing design (borrow) and alternate design (none) at each interim analysis when the simulated response rate is 0.45.

Effect	Interim 1		Interim 2		Final (0.99943)		Final (0.97706)	
	Borrow	None	Borrow	None	Borrow	None	Borrow	None
0	0.001	0.000	0.001	0.001	0.002	0.001	0.042	0.022
0.05	0.006	0.004	0.012	0.007	0.018	0.010	0.204	0.106
0.1	0.037	0.019	0.072	0.038	0.106	0.059	0.528	0.320
0.15	0.141	0.072	0.257	0.141	0.354	0.212	0.833	0.629
0.2	0.363	0.202	0.564	0.362	0.695	0.496	0.969	0.877
0.25	0.651	0.429	0.838	0.655	0.919	0.794	0.997	0.977
0.3	0.868	0.693	0.965	0.883	0.989	0.955	1.000	0.998

For a simulated treatment effect of 0.15, the borrowing design has 20% more power than the alternate design. Broken down by interim, the borrowing design is 7% more likely to declare success at the first interim, 12% more likely to declare success by the second interim, and 14% more likely to reach the higher threshold by the final analysis. The borrowing design is more likely to declare success when the simulated treatment effect is 0, with a 4.2% chance of declaring success compared to 2.2% for the alternate design.

Operating Characteristics Under Drop Out

Per the protocol, subjects who drop out of the mITT population prior to the final analysis for CDI related symptoms will be treated as treatment failures (regardless of arm). Therefore, simulated dropout has the practical effect of reducing the simulated control and treatment rates and the tables in the following second can be used to understand the performance of the design under a range of dropout scenarios.

For example, suppose that the true response rate on the control arm was 0.45, the true treatment effect was 0.20 and the dropout rate was 10%. Then, this trial would have the same operating characteristics of a trial with a simulated 0.405 control rate, a 0.145 treatment effect, and no dropout. The operating characteristics in this scenario can be adequately approximated using Table 8.

Additional Operating Characteristics

This section contains operating characteristics for control response probabilities in $\{0.2, 0.3, 0.4, 0.5, 0.6, 0.7\}$. A description of these tables can be found under the operating characteristics section.

Table 6: Operating when the underlying control response probability is 0.2

Effect	Interim 1		Interim 2		Final analysis	
	Pr(Success)	Pr(Futility)	Pr(Success)	Pr(Futility)	Pr(Success) (0.99943)	Pr(Success) (0.97706)
0	0.000	0.462	0.001	0.732	0.001	0.050
0.05	0.003	0.225	0.009	0.449	0.015	0.203
0.1	0.015	0.087	0.044	0.208	0.077	0.466
0.15	0.054	0.026	0.146	0.070	0.241	0.740
0.2	0.153	0.005	0.353	0.015	0.515	0.919
0.25	0.346	0.001	0.629	0.002	0.790	0.986
0.3	0.608	0.000	0.862	0.000	0.949	0.999

Table 7: Operating when the underlying control response probability is 0.3

Effect	Interim 1		Interim 2		Final analysis	
	Pr(Success)	Pr(Futility)	Pr(Success)	Pr(Futility)	Pr(Success) (0.99943)	Pr(Success) (0.97706)
0	0.000	0.539	0.000	0.811	0.001	0.025
0.05	0.002	0.301	0.004	0.571	0.007	0.114
0.1	0.010	0.122	0.026	0.285	0.044	0.347
0.15	0.049	0.033	0.119	0.089	0.189	0.679
0.2	0.172	0.006	0.353	0.016	0.495	0.912
0.25	0.419	0.001	0.674	0.002	0.812	0.988
0.3	0.710	0.000	0.901	0.000	0.964	0.999

Table 8: Operating when the underlying control response probability is 0.4

Effect	Interim 1		Interim 2		Final analysis	
	Pr(Success)	Pr(Futility)	Pr(Success)	Pr(Futility)	Pr(Success) (0.99943)	Pr(Success) (0.97706)
0	0.000	0.506	0.001	0.788	0.001	0.027
0.05	0.003	0.246	0.007	0.495	0.011	0.152
0.1	0.023	0.084	0.050	0.204	0.076	0.454
0.15	0.103	0.019	0.199	0.051	0.286	0.784
0.2	0.294	0.003	0.489	0.007	0.628	0.955
0.25	0.575	0.000	0.790	0.001	0.891	0.995
0.3	0.827	0.000	0.951	0.000	0.984	1.000

Table 9: Operating when the underlying control response probability is 0.5

Effect	Interim 1		Interim 2		Final analysis	
	Pr(Success)	Pr(Futility)	Pr(Success)	Pr(Futility)	Pr(Success) (0.99943)	Pr(Success) (0.97706)
0	0.001	0.389	0.002	0.668	0.003	0.063
0.05	0.010	0.166	0.019	0.358	0.027	0.260
0.1	0.054	0.049	0.101	0.123	0.143	0.595
0.15	0.187	0.009	0.316	0.025	0.418	0.869
0.2	0.431	0.001	0.626	0.003	0.748	0.978
0.25	0.700	0.000	0.870	0.000	0.938	0.998
0.3	0.885	0.000	0.971	0.000	0.992	1.000

Table 10: Operating when the underlying control response probability is 0.6

Effect	Interim 1		Interim 2		Final analysis	
	Pr(Success)	Pr(Futility)	Pr(Success)	Pr(Futility)	Pr(Success) (0.99943)	Pr(Success) (0.97706)
0	0.004	0.296	0.006	0.559	0.007	0.108
0.05	0.022	0.117	0.038	0.269	0.052	0.351
0.1	0.089	0.035	0.153	0.089	0.205	0.671
0.15	0.241	0.007	0.384	0.019	0.490	0.894
0.2	0.475	0.001	0.670	0.003	0.789	0.981
0.25	0.733	0.000	0.894	0.000	0.957	0.999
0.3	0.925	0.000	0.986	0.000	0.998	1.000

Table 11: Operating when the underlying control response probability is 0.7

Effect	Interim 1		Interim 2		Final analysis	
	Pr(Success)	Pr(Futility)	Pr(Success)	Pr(Futility)	Pr(Success) (0.99943)	Pr(Success) (0.97706)
0	0.004	0.290	0.007	0.555	0.009	0.108
0.05	0.021	0.120	0.036	0.279	0.049	0.325
0.1	0.082	0.033	0.141	0.086	0.197	0.661
0.15	0.246	0.005	0.396	0.013	0.529	0.919
0.2	0.559	0.000	0.760	0.001	0.880	0.995
0.25	0.877	0.000	0.977	0.000	0.995	1.000
0.3	1.000	0.000	1.000	0.000	1.000	1.000

Computational Details

Simulations were run using R (R Core Team 2017) version 3.4.3. Bayesian computations were performed using the Stan (Stan Development Team 2018) version 2.17.2.

Many samples from the posterior distribution are required to determine whether the posterior probability is greater than 0.99943 with sufficient precision. For the power calculations, for each trial we ran a single MCMC sampler for 10,000 iterations. When executing the trial, if the posterior probability of a positive treatment effect is close to the boundary we recommend using more samples to obtain sufficient precision. For example, using 1,000 independent Markov chains with 10,000 post burn-in iterations each.

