4.4 Determination of Sample Size

To demonstrate a 69% success with one dose of the RBX2660 treatment group vs. 47% success in the Placebo control group, 240 subjects are required (power > 90%, nominal 2.5% type I error rate). Up to an additional 30 subjects will be enrolled to allow for a 10% loss-to-follow up rate, for a total of approximately 270 subjects. Considering the 2:1 randomization, this results in approximately 180 subjects in the RBX2660 arm and 90 subjects in the Placebo arm. Enrolled subjects who have signed consent and withdraw for any reason prior to administration of the first blinded enema will be replaced without counting toward the sample size cap. Replacement subjects will be randomized to ensure proper blinding.

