6.3.2 Modified Intent-to-Treat Population

For the Modified Intent-to-Treat (mITT) population, subjects will be analyzed according to the randomized treatment assignment despite any treatment misallocations.

Additionally, the mITT population will be defined as all randomized subjects who successfully received blinded treatment but excluding;

- subjects who withdrew prior to treatment;
- subjects in whom treatment was attempted but not completed and;
- subjects who discontinue from the study prior to evaluation of treatment failure/success for the primary endpoint if the reason for exit is not related to CDI symptoms. Reason for exit will be captured on the exit form to allow for identification of such subjects.

Examples of reasons unrelated to CDI symptoms may include;

- Withdrawal of consent
- Death unrelated to CDI

Subjects who were exited prior to the 8-week efficacy assessment due to CDI related symptoms will be counted as treatment failures even if documentation as required per the protocol is not on file for the treatment failure.

The mITT population will be used for the primary efficacy reporting purposes. The mITT population will also be used for secondary and exploratory endpoints evaluation. The analysis of the ITT and PP populations may also be provided in addition to the mITT for purposes of regulatory evaluation.

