The trial will stop for futility at either interim if the predictive probability (PP) of success at the final analysis is sufficiently small. The predictive probabilities will be computed using a final threshold of 0.97706 and assuming a final enrollment of 270 subjects. Bayesian predictive distributions incorporate the uncertainty around the model parameters as well as the uncertainty in the outcomes of subjects not yet enrolled. The trial will stop for futility if there is limited probability that the trial will reach the success criterion, even at the maximum sample size. The criteria for declaring futility at each interim are shown in Table 3.

Table 3: Futility criteria at each analysis.

Analysis	Criteria	Subjects complete
Interim 1	PP(Success) < 0.01	Minimum 160
Interim 2	PP(Success) < 0.01	220

Strength of the Borrowing

The hyper-priors on τ_α^2 and τ_θ^2 are chosen to encourage dynamic borrowing from the Phase 2b trial. Dynamic borrowing is the idea that when the observed data in the current trial is similar to the previous trial, the strength of our conclusions should increase. On the other hand, if the newly observed data is quite different from the previous data, the prior data should contribute less information to our inference.

Consider two extremes. The first is the case of full borrowing, where data from the previous study is added to data from the new trial and inference is performed using the full weight of both studies. Alternatively, we could do no borrowing, ignoring information from the previous trial and conducting our analysis with only the new information. The hyper-priors on τ_α^2 and τ_θ^2 are specified to provide dynamic borrowing, behaving similarly to the full borrowing approach when the observed data resembles the Phase 2b data and mimicking the no borrowing approach when the results differ in the two trials. The effect of the dynamic borrowing is illustrated in Figure 1.

Figure 1: Effective sample size (ESS) borrowed on the treatment arm for different observed treatment and response rates at the first interim.

[figure not shown]

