In this example, the first interim analysis occurs when 180 subjects have been enrolled. The observed control rate is 0.5, somewhat higher than seen in the Phase 2b trial. Example 3.1 shows the status of the trial at the first interim

[figure not shown]
Example 3.1: Status of the trial at the 1st interim

The posterior estimate of the control response rate (0.473) is somewhat lower than

[figure not shown]
observed due to the borrowing and the posterior probability of a treatment effect is insufficiently high to declare success at the first interim.

Example 3.2: Status of the trial at the 2nd interim

At the second interim (N=220, shown in Example 3.2), the observed response rates in both arms have been reduced. The trial has not shown sufficient evidence to declare success or futility and continues enrollment, though the predictive probability of success at the final analysis remains optimistic (0.797).

Example 3.3: Status of the trial at the final analysis

The final analysis is conducted when 270 patients have completed follow-up and 260 subjects qualify for the mITT population (Example 3.3). The single trial success criteria is updated to 0.99931, using the information fraction and 0.99943 criteria at the first two interims (0.692 and 0.846) to ensure an overall α –spend of 0.00125. The trial is declared a success at the 0.025 level, though it does not meet the single trial success criteria.

Performance Characteristics

The performance characteristics of the design were determined through trial simulation. We assume several scenarios for the underlying response probability for the control and treatment arms, considering control probabilities in $\{0.2, 0.3, 0.4, 0.45, 0.5, 0.6, 0.7\}$ and additive treatment effects of $\{0.0, 0.05, 0.1, 0.15, 0.2, 0.25, 0.3\}$. The scenario with a control probability of 0.45 and a treatment effect of 0.15 corresponds most closely to what was observed during the Phase 2b trial. The scenarios with treatment effects of 0 correspond to null scenarios. For the purposes of simulation, we assume that patients are randomized in 3 patient blocks, that interim analysis were performed with exactly 160 and 220 subjects completed, and that the 270 mITT subjects have complete data at the final analysis.

Operating Characteristics

We simulated 1,000,000 virtual trials for each scenario. The results of the simulations are summarized using the following operating characteristics.

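### The simulated power tables and the futility prediction assume that all 270 treated subjects stay in the mITT, which fails once anyone is excluded; the effect is small

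*SAP*

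**What the plan says.** The Performance Characteristics section of the SAP appendix fixes the sample sizes behind its operating-characteristic tables. It assumes "that interim analysis were performed with exactly 160 and 220 subjects completed" and "that the 270 mITT subjects have complete data at the final analysis". This covers Tables 4 and 6 to 11 (the number 6 is used twice). The Futility Stopping section says the predictive probability is "computed using a final threshold of 0.97706 and assuming a final enrollment of 270 subjects".

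Three other places bear on whether 270 is attainable:

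- SAP 4.1 and Protocol 3.2 cap the number treated with a blinded enema at 270.
- SAP 4.4 sizes the trial at 240 and adds: "Up to an additional 30 subjects will be enrolled to allow for a 10% loss-to-follow up rate".
- SAP 6.3.2 removes from the mITT subjects whose administration was not completed. It also removes those who leave before the endpoint is evaluated "if the reason for exit is not related to CDI symptoms". CDI-related exits stay in and count as failures.

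The appendix acknowledges under Success Criteria that the final mITT may be below 270, and Example 3.3 has 260. It carries this only into the updated single-study threshold at the final analysis. The drop-out section says that "simulated dropout has the practical effect of reducing the simulated control and treatment rates"; N does not change there.

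**The concern.** With 270 treated at most, 270 complete mITT subjects requires that nobody is excluded. Any exit unrelated to CDI, or any incomplete enema, takes the trial off the scenario that was simulated. The drop-out section offers the tables for a range of dropout scenarios, but they can represent only exits counted as failures. They cannot show a smaller N.

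Two things are at stake. The tables are the only quantified power for the primary Bayesian analysis at its two success levels: the single-study threshold (0.99943, updated at the final look) and the lower threshold (0.97706). If N is smaller, that power is overstated. The futility rule also credits the trial with more future subjects than it can have, so it lets more null trials continue.

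**Working it through.** **Inputs.** Looks at 160, 220 and a final N, randomized 2:1; Phase 2b data 19/44 (placebo) and 25/42 (one dose); thresholds 0.99943 and 0.97706; futility if "PP(Success) < 0.01" (Table 3). The variance priors convert, with shape = weight/2 and scale = location² × weight/2, to 0.05 and 5×10⁻⁸ for the control term and 0.005 and 5×10⁻⁷ for the treatment term. The posterior was computed on a grid for every outcome, and exact binomial probabilities were carried through the three looks.

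**Range of the final mITT.** All 10% excluded: 270 × 0.9 = 243. All 10% kept as failures: 270. The split is an assumption, because the documents give none.

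**Reproduction and effect of exclusions (control 0.45).** The single-study column at 243 uses the updated final threshold of 0.99931.

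| | Lower, effect 0.10 | Lower, 0.15 | Lower, 0.20 | Single-study, 0.15 | Single-study, 0.20 |
|---|---|---|---|---|---|
| SAP Table 4 | 0.528 | 0.833 | 0.969 | 0.354 | 0.695 |
| Recomputed, 270 | 0.527 | 0.832 | 0.968 | 0.348 | 0.690 |
| Recomputed, 243 | 0.496 | 0.802 | 0.957 | 0.320 | 0.650 |

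The threshold update was checked on Example 3.3: information fractions 180/260 = 0.692 and 220/260 = 0.846 give 0.99931, as the SAP states. At an mITT of 260, lower-threshold power at effect 0.15 is 0.821, and the single-study figures also fall by about a point or less. At the planning rates of 69% and 47%, going from 270 to 243 moves the lower threshold from 0.988 to 0.983 and the single-study threshold from 0.821 to 0.787.

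**If some or all of the 10% are failures (lower threshold, effect 0.15).**

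- All failures, N = 270: rates 0.45 × 0.9 = 0.405 and 0.60 × 0.9 = 0.54; power 0.703.
- Half and half: 13.5 excluded leaves 256.5 (run at 256), with rates multiplied by 1 − 13.5/256.5 = 0.947; power 0.753.

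**Headline power in SAP 4.4.** Power = Φ[(Δ − 1.96·SE₀)/SE₁]. With 80 and 160 subjects, the pooled rate is (37.6 + 110.4)/240 = 0.617, SE₀ = 0.0666 and SE₁ = 0.0667. Then (0.22 − 0.1305)/0.0667 = 1.34, so power is 91.0%. At 81 and 162 it is 91.4%.

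**Futility.** Suppose the full 10% is excluded. Interim 2, at 220 mITT subjects, comes after about 220/0.9 = 244 have been treated and counted or excluded. Of the 26 left under the cap, 26 × 0.9 ≈ 23 will be evaluable. The rule credits 270 − 220 = 50.

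| Prediction N | Null (0.45) futility by interim 2 |
|---|---|
| 270 | 0.716 (SAP Table 4: 0.732) |
| 260 | 0.753 |
| 243 | 0.832 |

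With 33/73 placebo responders at interim 2, continuing needs at least 72/147 RBX2660 responders when predicting to 270 and at least 75/147 when predicting to 243. At a final mITT of 243, changing the prediction N moves power by less than 0.001 and leaves type I error at 0.041.

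**Limit of the check.** Null futility at interim 1 came out at 0.388, against 0.445 in Table 4, so that figure was not reproduced. Power is not sensitive to this, but the futility results are better read as differences than as exact rates.

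**The case against.** The strongest reply is that nothing was miscalculated. The tables reproduce at 270, that number is disclosed as a simulation assumption, the appendix admits the mITT may be smaller, and it updates the single-study threshold accordingly. This stands: the gap is a missing scenario, not an arithmetic error. But updating the threshold protects alpha; it does not restate power or change the prediction N.

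A second reply is that the rule is meant to ask whether success is improbable even at the maximum sample size, so leaning toward continuation is deliberate. That partly stands. A best case is a legitimate choice, but 270 is not the maximum mITT once a subject has been excluded.

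A third is that the Primary Analysis Population section treats mITT dropouts as failures, which would keep N at 270. It does so only for those in the mITT, and SAP 6.3.2 takes non-CDI exits out.

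A reader might also infer more than the documents support:

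- That the claim of more than 90% power is wrong. It rests on 240, and the extra 30 are the loss allowance; it holds at 243.
- That 243 is the expected mITT. It is the bound with the whole 10% excluded. At 260, the SAP's own example, the power loss is about a point or less and the gap in null futility is about 4 points.
- That the futility rule damages the trial's error rates. It does not; the cost is at most some further enrolment in null trials.

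**Conclusion.** The point holds as a minor one. Tables 4 and 6 to 11 and the futility prediction rest on an mITT of 270 that the treatment cap cannot supply if anyone is excluded. At the 243 bound with control 0.45, power is overstated by about 3 points at the lower threshold for effects of 0.10 to 0.15, about 1 point at 0.20, and 3 to 4 points at the single-study threshold. Exits kept as failures cost more, down to about 0.70 at effect 0.15 if they make up the whole 10%. The drop-out section already describes that mechanism, so the missing piece is the reduction in N. Predicting futility to 270 lowers null stopping by interim 2 by about 4 points relative to 260 and about 12 relative to 243. These sizes assume a realised 10% loss where 243 is used, no difference in loss between arms, and the 0.01 futility cutoff.

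**What to change.** - **Reconcile the futility cutoff first.** Table 3 gives 0.01 and the Example Trials text gives 0.001. At 0.001, null stopping by interim 2 would be about 59% predicting to 270 and 77% predicting to 243.
- **Re-run and restate the tables** at final mITT 243 and 260, with the correspondingly updated single-study threshold and a stated split of the 10% between exclusions and failures.
- **In Futility Stopping, replace 270** with the attainable final mITT: current mITT, plus the treated subjects still pending and the remaining treatable subjects, multiplied by the blinded pooled evaluable fraction.
- **In the drop-out section, state that non-CDI exits reduce N.** Correct its worked example at the same time: 10% failures applied to 0.45 and 0.65 gives 0.405 and 0.585, an effect of 0.18 rather than 0.145.

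The cost is one simulation re-run, an appendix edit and slightly lower stated power. Neither the enrolment cap nor the SAP 4.4 calculation needs to change.
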